1.0 PROTOCOL SUMMARY AND/OR SCHEMA

This is a blinded randomized control trial comparing a four week treatment with the antibiotic rifaximin versus placebo in the management of bowel dysfunction after Anterior Resection (AR) or Sphincter Preserving Surgery (SPS) for rectal cancer. Patients will be randomized into 2 groups, one group will receive rifaximin 400mg bid for 4 weeks and the other group will receive a placebo bid for 4 weeks. Prior to commencement of treatment patients bowel symptoms will be assessed using the MSKCC Bowel Function Instrument (BFI score). For those patients that agree, stool samples will be taken and stool bacterial content will be assessed. The same patients will also undertake breath testing to assess Small Intestinal Bacterial Overgrowth (SIBO). Following treatment, all patients will again be assessed using the BFI, and stool sampling and breath testing will be preformed on those patients that agreed to it. Four weeks after cessation of treatment all patients will undertake a third round of testing using the BFI and in respective patient, a third round of stool sampling and breath testing will occur. 1-24months following completion of the study, we will ask patients to participate in a follow up study using metronidazole 500mg po tid x 3 weeks on a voluntary basis. In this case we will use a phase II design and not compare with a placebo control.

The primary objective of this study is to compare the efficacy of rifaximin and placebo in the treatment of bowel dysfunction as measured by MSKCC Bowel Function Instrument in patients following AR or SPS for rectal cancer. A study schema is depicted below.

Memorial Sloan Kettering Cancer Center
[name]
[name]

2.1 OBJECTIVES AND SCIENTIFIC AIMS

2.2 Primary objective.

- To compare the efficacy of rifaximin and placebo in the treatment of bowel dysfunction as measured by MSKCC Bowel Function Instrument (BFI score) in patients following AR or SPS for rectal cancer.

2.3 Secondary objectives

- To determine if reduction in intestinal bacterial quantity correlates with improvement in bowel symptoms (BFI score).
- To explore the bacterial composition of stool before and after antibiotic treatment.
- To identify dynamic changes in bowel function during and after antibiotic treatment using a bowel function log.
- To identify the efficacy of metronidazole in the treatment of bowel dysfunction as measured by the MSKCC BFI in patients following AR or SPS for rectal cancer for patients who have no improvement following treatment with rifaximin or placebo.

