Appendix 2. Patients will then be invited to undertake a hydrogen breath test and fecal

sampling to assess for bacterial content in their small intestine and stool. Following stratification of patients by the method of anastomosis (stapled or hand sewn), the patients will then be randomized into two groups. The patients will receive treatment with rifaximin or placebo depending on the arm of the trial to which they have been randomized. Patients will at this stage on a volunteer basis be asked to submit stool samples and undertake a breath test. Patients will receive the respective treatment for four weeks. Following cessation of treatment all patients will be assessed using the BFI and respective patients will have repeat stool sampling and breath testing. Patients will then have these tests repeated 4 weeks later. This corresponds to 8 weeks after the start of the trial. For those patients not undertaking stool and breath testing, they will be reminded by phone, mail or email to fill out the BFI. Before and during the trial patients will be asked to fill out a weekly stool diary to evaluate trends on bowel function.

Appendix 3. Both the patients and the physicians will be blinded to the patient treatments. The Initial consultation along with subsequent rounds of testing with submission of stool samples and breath testing will be undertaken by one of the consenting physicians at a specifically arranged and designated “research clinic” at one of MSKCC’s network centers. (Sleepy Hollow, Commack, Main Campus and 53rd St). Patients may also be seen and consented at their regular follow up colorectal clinic visits. At 1 – 24 months after completion of the phase III portion of the trial, patients will be contacted by phone and given the option of receiving metronidazole in a followup, single arm study in which all patients receive the antibiotic. Patients who wish to participate will be mailed a drug prescription for a 3 week course of metronidazole 500mgs tid as well as the BFI forms and stool diary. Pretreatment and posttreatment BFI scores will be collected and analyzed for change in bowel function as was done in the initial Phase III study.

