4.3 Intervention

The antibiotic used will be rifaximin. Rifaximin acts by inhibition of bacteria synthesis of RNA. It is active against gram positive and gram negative bacteria including both aerobes and anaerobes however it is not absorbed in the gastro-intestinal system facilitating its use in enteric infections. It is licensed for the treatment of acute bacterial diarrhea and SIBO. [21] We have chosen to use rifaximin over metronidazole because it is not enterically absorbed and as such has less of a side-effect profile. Metronidazole causes a higher incidence of nausea and GI upset, has a greater amount of drug interactions and it also has a metallic taste which could effect blinding and introduce bias.

For this trial, both rifaximin and placebo will be prepared in identical capsules by the research pharmacist at MSKCC and distributed to the outpatient pharmacies. We have chosen a rifaximin dose of 400 mg bid for 4 weeks as this has been shown to be efficacious in the treatment of SIBO at this dose over 14 days. We have added a further

2 weeks to the treatment regime as from prior experience by the PI's using rifaximin in this condition, the beneficial effect tends to reduce over one week. As the BFI is validated for use over a 4 week period (ie assessing bowel function over a 4 week period), to show an effect on bowel function as assessed by the BFI, treatment is needed over a four week period. We plan to assess bowel function at 4 weeks after the completion of treatment to determine if the response to treatment is transient or whether it is a more durable effect. Following the completion of the trial patients will be offered a 3 week treatment with 500 mg of metronidazole tid. They will be assessed with the BFI at pretreatment and again at 0-1 and 4-6 weeks post treatment. Should the effect be transient, this will lead to future studies to assess if adding extra treatment with other medications such as pro-biotics may prolong the effect.

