7.0 RECRUITMENT PLAN

Patients who have had an anterior resection for rectal cancer at MSKCC will be identified from a prospective database maintained by the Colorectal Surgery Service. These patients will be contacted by a letter inviting them to participate in a randomized study designed to evaluate the beneficial effects of rifaximin and placebo on bowel function. **Appendix 1.** We will ask patients to participate in the trial based on their own personal perception of their symptoms. Patients will be asked in the letter to contact [name] (PI) or [name] (Research Fellow) by email, telephone, or letter. Patients who have not responded to the letter after one month will be contacted by phone and invited to participate. **Appendix 4.** Every attempt will be made to recruit women and minorities to participate in this study. Participation is voluntary. Patients who are interested in participating will be scheduled for a research clinic visit with [name] or another of the consenting professionals. Consenting patients will be registered and randomized at the initial clinic visit. We hope to recruit 70 patients, 35 in each arm in an attempt to have at least 30 patients per arm for analysis allowing for patient dropout.

Patients will also be asked to volunteer to submit stool samples and breath tests. Those who agree will be tested for stool bacteria and SIBO at the relevant time points along with the MSKCC BFI. For those patients who do not agree to volunteer to supply stool samples and breath test, they will be tested using the MSKCC BFI alone at the relevant time periods. All patients will fill out the stool log/diary. We hope to recruit half of the patients in each arm to participate in the extra testing. We are not testing all patients with stool sampling and breath tests as we feel it will hamper accrual into the trial. Patients will be reimbursed with a \$100 gift card for each outpatient visit to cover transport costs for participating in this trial. Following completion of the phase III portion of the trial, patients will be contacted by phone and offered to participate in a follow up single arm study to assess the efficacy of metronidazole in the treatment of bowel dysfunction.

Memorial Sloan Kettering Cancer Center
[name]
[name]

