Patients already enrolled on version A(0) or A(1) will also be asked via phone to participate in the follow up study. If they wish to participate, they will be reconsented. Consent forms will be mailed to them with a self addressed return envelope.

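### The metronidazole objective is limited to patients with no improvement, but neither enrolment nor analysis applies that limit and the term is not defined

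*Combined protocol and SAP*

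**What the plan says.** Section 2.3 lists, as the last secondary objective, the efficacy of metronidazole measured by the BFI "for patients who have no improvement following treatment with rifaximin or placebo".

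The sections that describe who enters this follow-up carry no such condition:

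- Section 1.0: "we will ask patients to participate in a follow up study using metronidazole 500mg po tid x 3 weeks on a voluntary basis". The same section calls this part a phase II design without a placebo comparison.
- Section 4.2: patients are phoned 1 to 24 months after the phase III portion, and those who wish to take part are mailed a prescription.
- Section 4.3: "Following the completion of the trial patients will be offered a 3 week treatment".
- Section 7.0: "patients will be contacted by phone and offered to participate in a follow up single arm study to assess the efficacy of metronidazole". Patients enrolled under earlier protocol versions "will also be asked via phone to participate in the follow up study".
- Section 10.1: the offer is repeated in similar terms, with BFI at pretreatment and at days 21-30 and 49-63 after starting metronidazole.

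The eligibility criteria in Sections 6.2 and 6.3 do not mention earlier response. The only analysis statement is in Section 4.2: "Pretreatment and posttreatment BFI scores will be collected and analyzed for change in bowel function as was done in the initial Phase III study". Section 14.0 does not mention metronidazole. Section 12.0 names the BFI as the response measure but gives no cut-off.

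**The concern.** The objective names one population, and the enrolment and analysis text produces another. A team following the plan would enrol any willing trial patient, pool the pre/post BFI changes, and have one number to report against an objective about non-improvers. That number mixes patients who had already improved with patients who had not.

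The undefined term adds a second problem. The plan does not say whether improvement is judged by the BFI or by patient report, at which assessment, or against what cut-off. The time point matters because Section 4.3 reports that, from prior experience with rifaximin, "the beneficial effect tends to reduce over one week". A patient could therefore count as improved at days 26-35 and not at days 53-63. If these choices stay open, the subset can be chosen after the results are known.

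**Working it through.** **Inputs (Section 14.0):** mean BFI change 0 on placebo and 5.8 on rifaximin, SD of change 8, 30 patients per arm, two-sided 5%. Assumed here: changes are normally distributed.

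**The plan's own figure.** Power by the normal approximation = Φ(5.8 / (8 × √(2/30)) − 1.96) = 0.802. This agrees with the stated 80%, so the inputs are read as intended. The plan gives no sample size or power for the metronidazole part.

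**Share inside the objective.** For a cut-off c, the proportion classed as not improved is Φ(c/8) on placebo and Φ((c − 5.8)/8) on rifaximin. Two readings are tried: the literal one (change of 0 or less) and a change below 6. Six points is the only BFI difference the plan calls meaningful. It comes from comparing anastomosis groups and is not stated as a within-patient threshold.

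| Reading | Placebo | Rifaximin | Qualify, of 60 | Outside |
|---|---|---|---|---|
| Change ≤ 0 | 0.500 | 0.234 | 30 × 0.734 = 22.0 | 63% |
| Change < 6 | 0.773 | 0.510 | 30 × 1.283 = 38.5 | 36% |

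**Does pooling change the conclusion?** As an illustration, let non-improvers change by 0 on metronidazole and improvers gain g on average, and let non-improvers volunteer r times as often as improvers. With q qualifying patients and 60 − q others:

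- n = q + (60 − q)/r
- w, the share of improvers, = ((60 − q)/r)/n
- pooled mean = w × g
- pooled SD = √(64 + g² × w × (1 − w))
- 95% half-width = t(0.975, n − 1) × SD/√n

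The values of g and r are assumptions. For g = 6:

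| Reading | r = 1 | r = 2 | r = 4 |
|---|---|---|---|
| Change ≤ 0 | 3.80 ± 2.20 (n = 60) | 2.78 ± 2.70 (n = 41) | 1.81 ± 3.05 (n = 32) |
| Change < 6 | 2.15 ± 2.20 (n = 60) | 1.31 ± 2.40 (n = 49) | 0.74 ± 2.51 (n = 44) |

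For g = 3 the interval includes 0 in all six cases; the closest is 1.90 ± 2.10 (change ≤ 0, r = 1). So the pooled interval excludes 0 in two of the twelve scenarios, one of them barely (2.78 − 2.70 = 0.08).

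**Precision of the subset.** With SD 8, half-width = t × 8/√n:

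- n = 22: 2.080 × 8/√22 = 3.5
- n = 39: 2.024 × 8/√39 = 2.6
- n = 60, all pooled: 2.001 × 8/√60 = 2.1

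**The case against.** The best defence is that anyone may enrol and the objective is meant to be read in the non-improver subset. This is a fair reading of Section 2.3, but no section describes such a subset analysis, and the subset could not be formed without a definition. The gap remains.

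A second defence is scale: this is the last secondary objective, in a voluntary follow-up that Section 1.0 already describes as lacking a placebo control. That stands and limits the weight of the point. It is also true that a definition could sit in the schema, consent form or appendices, which were not available. The mismatch between the objective and the body text does not depend on them.

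A reader might infer more than the documents support in four ways:

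- **That pooling would produce a false finding of efficacy.** This depends on the cut-off, uptake and gain assumed, and it occurs in only two of the twelve scenarios.
- **That the phase III ANCOVA, with its treatment term, would be fitted to one arm.** Section 1.0 rules out a placebo comparison and Section 4.2 speaks of change in bowel function, so a pre/post change is the natural reading.
- **That a 3-week course cannot register on the BFI**, because Section 4.3 says "to show an effect on bowel function as assessed by the BFI, treatment is needed over a four week period". The phase III window runs to day 35, when a four-week recall covers days 8-35 and hence 21 treated days (8-28). The plan already accepts that exposure, so this is not a separate flaw.
- **That the planned dropouts would be unclassifiable.** The follow-up is offered after completion of phase III, so they may never enter it. Section 10.1 provides phone follow-up of incomplete answers.

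**Conclusion.** The point holds as an internal contradiction. The objective is restricted to non-improvers, the enrolment and analysis text is not, and no available text defines the term. The result the plan would produce does not answer the stated objective.

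The mismatch covers roughly 36% to 63% of a fully enrolled group of 60. That range rests on Section 14.0's means and SD, on normality, and on the two cut-offs tried. It would be smaller if non-improvers volunteered more often: with a cut-off of 0, the share outside is 46% at 2:1 uptake and 30% at 4:1. The contradiction itself needs none of these figures.

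The primary comparison and its sample size are untouched. The plan should be corrected, but the matter is confined to one secondary objective.

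**What to change.** 1. Reconcile Section 2.3 with Sections 1.0, 4.2, 4.3, 7.0 and 10.1 on the population. Who should be offered the drug is a clinical decision, and this review takes no position on it.
2. If the offer stays open to all, define no improvement by measure, time point and cut-off, using BFI assessments already scheduled (baseline, days 26-35, days 53-63). Do this before unblinding and before any metronidazole BFI is examined. Report that subset as the objective's result and the other patients separately.
3. State in Section 14.0 that the analysis is the mean paired change in global BFI from metronidazole pretreatment to days 21-30, with a 95% CI, and that days 49-63 address durability. Describe it as an uncontrolled estimate.
4. Sections 9.0 and 17.1 allow open rifaximin after unblinding, possibly before metronidazole. Record such use and show the result with and without those patients.

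**Cost:** wording in the listed sections, one paragraph in Section 14.0 and one added data item, with no new BFI assessments. The price is precision: a half-width of about 3.5 points with 22 patients or 2.6 with 39, against 2.1 if all 60 are pooled (SD 8 assumed), and wider if fewer volunteer.

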3.0 BACKGROUND AND RATIONALE

The surgical treatment of rectal cancer has become increasingly directed towards sphincter preservation where possible, with the avoidance of a permanent stoma. This has been accomplished in part by refinement of the conventional anterior resection with surgical techniques such as ultra low anterior resection (LAR), intersphincteric dissection, and coloanal anastomosis (CAA). [1, 2] The widespread use of neo-adjuvant radiotherapy and chemotherapy has also led to the down staging of low rectal tumors pre-operatively which previously would have necessitated an abdomino-perineal resection again facilitating sphincter preserving surgery (SPS). [3]

The large number of patients treated by SPS has led to a greater awareness of the bowel dysfunction following surgery or so called anterior resection syndrome (ARS). [4] Up to 90% of patients develop symptoms of bowel dysfunction following SPS for rectal cancer. The most common symptoms include incomplete evacuation, clustering of bowel motions, food affecting frequency, unformed stool, and gas incontinence; the less common but more debilitating symptoms are stool frequency and incontinence. [5] Several surgical treatment factors are known to affect bowel function. In addition, the use of adjuvant or neo-adjuvant radiotherapy to the pelvis has also been shown to exacerbate these symptoms and worsen bowel function. [6, 7] These symptoms have a significant effect on patient quality of life with 27% of patients describing their symptoms as severely affecting their lifestyle and significantly impacting on their quality of life. [5] The mechanisms responsible for these symptoms are not clearly understood but are thought to involve a combination of etiological factors, including loss of fecal reservoir (rectum), injury to pelvic nerves and sphincter injury. [8-11] A variety of novel surgical techniques have been developed with the goal of minimizing bowel dysfunction: these include creation of a neo-rectum using a colonic-J-pouch, coloplasty, end to side colorectal anastomosis, construction of artificial anal sphincters, and sacral nerve stimulation. [7, 12] These methods have been met with varying degrees of success; however, none have resulted in completely satisfactory bowel function. [13] Currently there is no standard of care for the medical management of this bowel dysfunction. Patients are generally treated individually based on symptoms

with a combination of high fibre diet, antidiarrheal agents, laxatives and/or probiotics without significant success.

Another theory explaining ARS is that denervation of the distal colon and reduction of rectal volume leads impaired / inefficient rectal evacuation and a state of rectal pseudo-obstruction. The resulting stasis of stool within the colon leads to increased numbers of colonic bacteria and subsequently overgrowth of bacteria in the large and small bowel contributing to the symptoms of bowel dysfunction.

Altered bowel function as a consequence of increased intestinal bacteria is not a new concept. Antibiotics are used in many intestinal conditions to improve bowel function. Patients with Crohns disease and small intestinal bacterial overgrowth SIBO have been shown to benefit from treatment with metronidazole and rifaximin individually, with both a reduction in SIBO and bowel symptoms.[14, 15] In active inflammatory bowel disease, antibiotic therapy also plays a role in its management. Metronidazole appears to induce significant clinical improvement in patients with pouchitis compared to placebo,[16] and long term treatment using rifaximin and metronidazole reduces the incidence of clinical flare ups of IBD again as compared to placebo.[17, 18] Similarly in irritable bowel syndrome, treatment with rifaximin has demonstrated both improvement in symptoms and a reduction in SIBO.[19] Finally in patients with chronic liver disease antibiotics again specifically both metronidazole and rifaximin have been used to reduce ammonia producing bacteria in the intestine and with that the incidence of hepatic encephalopathy and spontaneous bacterial peritonitis.[20]

Within the past two years, the PI has used metronidazole (500mg po tid for 14 days) to treat severe bowel symptoms in over 20 patients. Over 80% of these rectal cancer patients have reported marked improvement in their bowel function, including better stool formation, more complete evacuation, fever bowel motions, and less gas formation. No adverse effects were noted. However, after stopping metronidazole bowel symptoms were noted to return gradually over one to two months. More recently the PI has begun treating patients with rifaximin 400mg bid as it has fewer side effects, with similar results. This experience has led us to the theory that by treating patients with antibiotics the quantity of fecal bacteria is reduced, which in turn improves stool formation, enhances rectal evacuation, and alleviates the symptoms of bowel dysfunction.

4.1 OVERVIEW OF STUDY DESIGN/INTERVENTION

4.2 Design

Consented patients will undertake the MSKCC Bowel Function Instrument, a validated questionnaire developed by the Co-PI that assesses bowel function. [5]

Appendix 2. Patients will then be invited to undertake a hydrogen breath test and fecal

sampling to assess for bacterial content in their small intestine and stool. Following stratification of patients by the method of anastomosis (stapled or hand sewn), the patients will then be randomized into two groups. The patients will receive treatment with rifaximin or placebo depending on the arm of the trial to which they have been randomized. Patients will at this stage on a volunteer basis be asked to submit stool samples and undertake a breath test. Patients will receive the respective treatment for four weeks. Following cessation of treatment all patients will be assessed using the BFI and respective patients will have repeat stool sampling and breath testing. Patients will then have these tests repeated 4 weeks later. This corresponds to 8 weeks after the start of the trial. For those patients not undertaking stool and breath testing, they will be reminded by phone, mail or email to fill out the BFI. Before and during the trial patients will be asked to fill out a weekly stool diary to evaluate trends on bowel function.

Appendix 3. Both the patients and the physicians will be blinded to the patient treatments. The Initial consultation along with subsequent rounds of testing with submission of stool samples and breath testing will be undertaken by one of the consenting physicians at a specifically arranged and designated “research clinic” at one of MSKCC’s network centers. (Sleepy Hollow, Commack, Main Campus and 53rd St). Patients may also be seen and consented at their regular follow up colorectal clinic visits. At 1 – 24 months after completion of the phase III portion of the trial, patients will be contacted by phone and given the option of receiving metronidazole in a followup, single arm study in which all patients receive the antibiotic. Patients who wish to participate will be mailed a drug prescription for a 3 week course of metronidazole 500mgs tid as well as the BFI forms and stool diary. Pretreatment and posttreatment BFI scores will be collected and analyzed for change in bowel function as was done in the initial Phase III study.

